### Study outline

### **DATA AND SPECIMEN BANKING:**

All participant data will be closely safeguarded. Participants will be tracked in NITRO StudyTracker. REDCap will be used as the secure online database for the study. Qualitative data from interviews will be stored in secure drives on password-protected computers in a locked office. Extensive measures will be taken to ensure data confidentiality. Written informed consent will be obtained and consent forms will be maintained in a secure locked location that only research team personnel will have access to, as well as scanned per requirements. Use of REDCap will allow for quality control, as data can only be entered securely and with limited range. All team members will be trained on data security and confidentiality, and will ensure the safe management of data. No specimens will be banked for future use.

#### DATA AND SPECIMEN MANAGEMENT:

Data management: Extensive efforts will be made to protect the confidentiality of participants. No biological specimens will be collected. All data are in the form of survey responses, interview/focus group responses, medical record review, and SweetMama user data. All data will be stored in secure, locked offices in Prentice Women's Hospital or the Department of Obstetrics and Gynecology research facility on password-protected computers, and in REDCap, a secure, Northwestern-approved electronic data capture resource.

Participant contact information and protected health information will only be accessible to the research team. Following participant recruitment, a study ID will be assigned and survey/interview results will be deidentified. Paper surveys do not contain any PHI and will only be identified by this unique study identification number. Participant identifiable information will be separated (and stored in StudyTracker) from research information (which will be stored in secure computers and REDCap). Data will be transported from the point of collection (i.e. clinic or the CBITs usability lab) to secure electronic data storage locations via direct upload on secure laptops. [name] and the study team will have responsibility for data transmission and storage. Data stored on the secure, password protected computers will be password protected and stored on hospital servers with automatic backup and active, updated antiviral software. Data will be stored for 5 years after analysis is complete and then data will be permanently removed from the computers that they have been stored on. Access to data will only be granted to the PI ([name]) or the research assistants responsible for enrolling and entering data. Quality control will be assured via extensive training of research team members prior to patient recruitment. Further, information collected from the applications on the mobile phones will be transmitted to a secure server via encrypted, password-protected tunnels to protect users' privacy.

Sample size calculation: As this study is not a hypothesis-testing study but rather a usability/feasibility study, the sample size is not based on a statistical power calculation but on standard sample sizes for studies of this nature. Sample sizes were generated based on data illustrating that these sizes are sufficient to inform high quality user-centered design of a larger scale, next step behavioral intervention trial. For the pilot RCT phase, the sample size is set to provide sufficient data to make reasonable estimates regarding recruitment and feasibility but is not designed to assess clinical outcomes.

Analysis: This is a mixed methods analysis. Descriptive statistics using bivariable analysis will be used to characterize the study populations. For statistical comparisons, all tests will be two sided and p<0.05 will be considered statistically significant. All statistics will be performed using STATA 15. Analyses will be performed as follows:

- Focus groups and user interviews (including provider focus groups and interviews): During focus groups and user interviews, we will take detailed notes and audio record in order to capture participant feedback. After each group, the research team will construct a brief preliminary summary report. Transcripts will then undergo rigorous and reproducible qualitative analysis techniques using the constant comparison method. Analysis will be performed in Dedoose, a secure qualitative data management and analysis software that facilitates collaborative exploration of data and identification of themes in accordance with the Health Belief Model and Theory of Self-Efficacy. Dedoose has been previously used for multiple studies performed in our Department and has data security approvals by NUIT; only deidentified data will be uploaded to Dedoose. We will ensure reproducible and rigorous interpretations are accomplished via use of memos, creation of a consensus code list with clear operational definitions, and calculation of agreement statistics for inter-coder reliability. The final report will compare data gathered from focus groups and user interviews and summarize themes. We will then iteratively modify SweetMama based on these results.
- Individual testing: Analysis of individual data will consist of qualitative and quantitative analyses with the goals of identifying user feedback to incorporate participant needs into design and determining user features associated with greater satisfaction and use. The primary outcome will be user adherence, based on user interactivity data. Given the small study size and aim of assessing usability, the analysis of user interactivity data will be largely descriptive (i.e., no comparison group) but we will also examine the effects of potential mediating factors, such as health literacy and self-efficacy.

Secondary outcomes include both qualitative interview data and the quantitative data regarding use and patient characteristics, as described above. Qualitative data will be analyzed in the same manner as described above, with an additional mixed methods evaluation of interview data in concert with quantitative measures. Quantitative results for the SUS and USE will be used to assess satisfaction with and usability of SweetMama. User interaction data will be quantified to ensure tool functionality and determine areas for improvement. Using Stata v.15, we will perform bivariable and multivariable analyses to measure the relationships between baseline demographic/clinical characteristics, DES-SF, and PAM with user satisfaction and SweetMama interactivity.

- Provider surveys (in pilot RCT): Provider surveys will be analyzed using descriptive statistics as needed.
   We will analyze provider perceptions of engagement via the CSPAM and the modified CSPAM questions about SweetMama.
- Pilot RCT phase:
  - Qualitative and mixed methods: Exit interviews will use qualitative techniques and behavioral theories described above. We will use Dedoose software to perform a mixed methods analysis of themes in the context of quantitative measurements. For example, we will analyze satisfaction-related themes stratified by user interaction data such as quantity of episodes of active use, a measure of intervention exposure. This method allows us to assess several specific questions, such as if there are differences based on gestational age at enrollment or "dose" of intervention received.
  - O Quantitative: Using Stata, we will report baseline characteristics, recruitment and retention metrics (cumulatively and per month), and user interaction data. Outcomes will be compared a) within individuals (baseline vs. postpartum) and b) between groups (retention, behavioral measures and clinical outcomes). Bivariable analyses will be performed, with *a priori* subgroup analyses to assess differences by age, diabetes type, medication use/changes, and gestational age at entry (<20 weeks vs. ≥20 weeks). Regression modeling will be used to assess the relationship of SweetMama use to retention and other behavioral outcomes after controlling for potential confounders, such as length of exposure. Within the experimental group, although statistical power will be limited, we will also perform bivariable and multivariable analyses to assess relationships between user clinical/behavioral characteristics and satisfaction and use. Feasibility targets for study retention will be set at 80% retention in the study protocol. Feasibility target for SweetMama adoption will be 80% active use (defined as at least weekly interaction with SweetMama content). Targets are set at 80% based on prior literature using this threshold to represent greater engagement. 36,61

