# Feasibility testing: Pilot RCT (patient component)

After SweetMama is modified based the usability testing phase and provider feedback, which we anticipate will take 1-2 months, feasibility testing will occur with up to 50 eligible pregnant women via field testing. The goals of this phase are to field test recruitment, retention, and assessment strategies, as well as delivery of SweetMama within a pilot RCT, to assess feasibility and inform the design of a full trial assessing behavior, glycemic control, and perinatal outcomes. We will collect feasibility data regarding recruitment, technical challenges, quality assurance, and retention, as well as clinical outcomes data and patient-reported outcomes.

Women will be recruited to participate in the same manner as described above, via routine clinical interactions. Medical records will be reviewed for eligibility and women with diabetes will then be approached for verbal in-person screening and recruitment using a recruitment script (Appendix E). Participants will sign written informed consent. Enrolled women will be provided a "SweetMama timeline" document that explains the study activities, provides contact information, and outlines how to contact the team for technical help or any other needs. We will then randomized participants. Randomization, via REDCap, 76 will be unbalanced to

offer greater odds of receiving the experimental treatment in order to enhance the research team's experience with SweetMama and incentivize participation, with a target sample of 40 (randomized 1:3, stratified by DM type). The target sample size is 40, but up to 50 women may be enrolled in order to account for drop-out or the requirements of the randomization schema.

Women who are randomized to usual care will receive no orientation to or enrollment in SweetMama. They will receive surveys at enrollment, during the delivery hospitalization, and at the postpartum visit (see details in table below). Women who receive usual care will not undergo interviews.

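### A pilot that says it tests no hypotheses applies a blanket p<0.05 rule to about a dozen outcomes and four subgroup factors, with no multiplicity control or exploratory label

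*Combined protocol and SAP*

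**What the plan says.** In the current protocol (the version that contains the pilot RCT), the sample-size paragraph under Data and Specimen Management says "As this study is not a hypothesis-testing study but rather a usability/feasibility study, the sample size is not based on a statistical power calculation". It adds that the pilot sample is meant to "make reasonable estimates regarding recruitment and feasibility but is not designed to assess clinical outcomes". The Analysis paragraph that follows sets a single rule for all comparisons: "all tests will be two sided and p<0.05 will be considered statistically significant". It then introduces a list of analyses whose last item is the pilot RCT.

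The pilot's quantitative item compares outcomes within women, from baseline to postpartum, and "between groups (retention, behavioral measures and clinical outcomes"). It adds prespecified "subgroup analyses to assess differences by age, diabetes type, medication use/changes, and gestational age at entry", regression models relating SweetMama use to retention and behavioural outcomes, and analyses of associations inside the SweetMama arm. Only the last of these carries a warning about power.

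The section on the pilot RCT (patient component) describes randomisation "with a target sample of 40 (randomized 1:3, stratified by DM type"), and says that "up to 50 women may be enrolled in order to account for drop-out or the requirements of the randomization schema". It names feasibility and satisfaction as primary, with behavioural, clinical and glycaemic measures as secondary. The plan nowhere adjusts for multiplicity, ranks the secondary tests or labels the between-arm and subgroup comparisons exploratory.

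**The concern.** The two statements pull against each other. A study that declines to test hypotheses has no use for a significance threshold, yet the threshold is what will decide which pilot results are called statistically significant. With many outcomes, four subgroup factors and no adjustment, some of those labels would be expected by chance alone, including on glucose or neonatal outcomes that the sample is said not to be sized for. The pilot is intended to inform the design of the full trial, so mislabelled results could affect that design.

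Two further problems are separate from multiplicity. The small control arm makes the comparisons imprecise, so significance is a poor summary in either direction. And a subgroup defined by medication changes may be formed after randomisation, so that comparing arms within it would lose the protection of randomisation.

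**Working it through.** The plan gives no power figure, test count or familywise error rate, so there is no stated figure to reproduce. What follows is counted from its lists.

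**Arm sizes.** 40 at 1:3 gives 40/4 = 10 usual care and 30 SweetMama. At 50 enrolled, 50/4 = 12.5, so 12 or 13 controls.

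**Between-arm outcomes.** Retention (1), DES-SF (1), PAM (1), adherence (1), clinical measures (5: NICU admission, neonatal hypoglycaemia, birthweight, mode of delivery, hypertensive disorders) and glycaemic measures (3: last HbA1c, change in HbA1c, share of glucose readings outside goal). That is 12, or 13 if adherence counts as two measures. DES-SF and PAM are counted once although both are collected at delivery and again postpartum.

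**Expected false positives if nothing differs.** Expected number = 0.05 x m. Chance of at least one, if tests are independent = 1 - 0.95^m.

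| Tests counted | m | Expected | At least one |
|---|---|---|---|
| 12 outcomes, overall only | 12 | 0.60 | 46% |
| 13 outcomes, overall only | 13 | 0.65 | 49% |
| 12 outcomes, plus one test per factor (12 x 4) | 60 | 3.0 | 95% |
| 13 outcomes, plus one test per factor (13 x 4) | 65 | 3.25 | 96% |
| 12 outcomes, plus two levels per factor (12 x 4 x 2) | 108 | 5.4 | 99.6% |
| 13 outcomes, plus two levels per factor (13 x 4 x 2) | 117 | 5.85 | 99.8% |

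Baseline, within-person, adjusted-model and SweetMama-arm tests are left out and would add to these counts.

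**Correlation.** Expected counts do not depend on independence; the chance of at least one does. In a simulation of 12 normal outcomes in 10 and 30 women (1,500 replicates, even subgroup splits) with correlation 0.5 between outcomes, the expected counts stayed at about 0.6, 3.1 and 5.4 for m = 12, 60 and 108. The chance of at least one fell to 33%, 86% and 90%.

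**Exact tests.** The plan does not name the test for binary outcomes. Suppose five of the 12 are analysed as binary with Fisher's exact test, at assumed event rates of 10%, 20% and 50%. Its true size is then 0.017, 0.024 and 0.024 at 10 versus 30, and 0.005, 0.013 and 0.025 at 5 versus 15.
- 60 tests, using the 10-versus-30 size throughout as an approximation: 5 x (7 x 0.05 + 5 x size) = 2.2 to 2.4.
- 108 tests: (7 x 0.05 + 5 x size at 10 v 30) + 8 x (7 x 0.05 + 5 x size at 5 v 15) = 3.4 to 4.3.

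**Power (normal approximation, in SD units).** Standard error of a difference at 10 versus 30 = sqrt(1/10 + 1/30) = 0.365.
- True difference 0.5 SD: 0.5/0.365 - 1.96 = -0.59, power about 28%. At 0.8 SD, about 59%.
- 80% power needs (1.96 + 0.84) x 0.365 = 1.02 SD.
- The 95% interval extends 1.96 x 0.365 = 0.72 SD either side. A significant result must therefore show at least 0.72 SD, which is 0.72/0.5 = 1.4 times a true 0.5 SD difference.
- At 12.5 versus 37.5, the standard error is 0.327 and power for 0.5 SD is about 33%.
- At 5 versus 15 (an even split within a subgroup), 80% power needs about 1.45 SD.

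**Medication factor.** The pilot section says a woman who starts insulin after enrolment begins the insulin messages that week. In the SweetMama arm, then, a medication change alters the content received. Changes may also follow glucose control, which the app is meant to improve. A subgroup defined by such changes can differ between arms because of the allocation itself.

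**The case against.** **The count is not the plan's.** A reader might infer 117 tests. The documents do not support that as a fixed number: the subgroup sentence does not say that each outcome is tested in each level, and one test per factor is at least as natural. It prints two levels only for gestational age and gives none for medication. The thirteenth outcome is doubtful too, because the second part of the adherence definition nearly repeats a glycaemic measure. Glycaemic outcomes are also listed apart from clinical ones, so including them is an inference; without them, 9 outcomes give 9 x 5 x 0.05 = 2.25 with one test per factor. All this stands, and is why a range is given.

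**Ten controls do not cause false positives.** A reader might link the small arm to the expected chance findings. That would be wrong: a small arm does not raise the type I error rate, and exact tests lower it. Its effect is low power. The figure of 5 controls per level also assumes even splits, which the plan aims for in recruitment on some factors but does not guarantee within the control arm.

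**The main conclusions are protected.** The feasibility criteria are 80% targets, not p-values, and the plan twice says the pilot is not designed for clinical outcomes. A reader might infer that pilot effects will set the full trial's effect sizes, or that null results will be read as no effect. The plan says neither. What remains is that its caution about clinical outcomes is not carried into how p-values are to be read.

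**The medication point depends on a reading.** It applies only if arms are compared within the subgroup, which the plan leaves open.

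**Conclusion.** The concern holds. The sample-size paragraph and the significance rule are inconsistent for the pilot, and nothing elsewhere in the plan resolves this.

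Under no true effect, expected false positives are about 0.6 from the overall between-arm tests alone, and about 2 to 6 once subgroup tests are added. That range rests on 12 or 13 outcomes, one or two tests per subgroup factor, and nominal or exact tests. More than one expected chance finding therefore depends on the subgroup analyses.

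Low power is a distinct defect: about 28% for a 0.5 SD difference at 10 versus 30, so non-significant results are uninformative and significant ones are likely to be too large. The medication factor is a third, conditional problem. None of these touches the 80% feasibility criteria. The change is worth making because it alters what the pilot may claim about behaviour, glucose and clinical outcomes.

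**What to change.** In the Analysis paragraph, exempt the pilot RCT from the p<0.05 rule and state instead:

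- Between-arm, within-person and subgroup results are reported as estimates with 95% confidence intervals, labelled exploratory, with no claim of statistical significance.
- Feasibility continues to be judged against the existing 80% targets for retention and active use.
- Between-arm subgroups use baseline factors only. Medication at enrolment replaces medication use or changes, and changes during the study are described by arm without a subgroup comparison.

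An exploratory label on its own would remove the contradiction with less rewriting. Intervals also show how little 10 controls can establish, and they match the plan's stated aim of making estimates.

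The cost is a change of wording, with no new data. The downside is that no pilot comparison could be called significant.

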The primary outcomes of Aim 2 are feasibility (≥80% retention; see below) and satisfaction (USE, SUS, interviews). Secondary outcomes are behavioral (DES-SF, PAM, adherence), clinical (hypertensive disorders, delivery mode, birthweight, neonatal hypoglycemia, NICU admission), and glycemic control outcomes. Glycemic control will be assessed as hemoglobin A1c (final and difference from enrollment to delivery) and as proportion of blood glucose measures out of goal. Adherence will be assessed as proportion of prenatal visits attended and with available glucose data.

In order to assess these outcomes, the measures in the following table will be collected via the medical record, user interaction reports, and patient report:

All women		Additional data gathered in SweetMama arm	
Baseline	
 
Demographics, clinical data, eHEALS, NVS, DES- SF, PAM, technology comfort questionnaire
 
		
Monthly	
 
Retention (continuation in care and the study protocol)
 
	
 
SweetMama retention and adoption
 
SweetMama functionality, quality assurance & content feedback (technical check-ins)
 
	
Delivery	
 
Retention (continuation in care and the study protocol)
 
	
 
SweetMama functionality, quality assurance, & content feedback
 
Exit interview- feasibility, improvement, and engagement
 
	

	Treatment adherence		•	Satisfaction and usability: USE and SUS
	•	Behavioral measures: DES-SF, PAM	•	User interaction data (see Aim 1)
	•	Maternal and neonatal clinical data		
Postpartum	•	Behavioral measures: DES-SF, PAM	
 
Exit interview part 2 – postpartum curriculum - feasibility,
 
	
				improvement, and engagement

As in the usability testing phase, we will collect baseline information on (see details above):

- Demographic and clinical characteristics
- Electronic health literacy measured the eHealth Literacy Scale (eHEALS)65
- Health literacy measured via the Newest Vital Sign
- Diabetes self-efficacy measured via the Diabetes Empowerment Scale–Short Form (DES-SF
- Patient activation measured via the Patient Activation Measure (PAM)
- Technology comfort Using a modified version of the Technology Comfort Questionnaire (12 items), we will ask about smartphone familiarity and comfort.

We will also collect data from study and medical record upon completion on:

- Retention, measured as continuation in the study protocol

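### Pilot RCT arm comparisons of DES-SF, PAM and A1c name neither the outcome's baseline value nor the DM-type stratum as covariates; naming them is a free, modest gain in precision

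*Combined protocol and SAP*

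**What the plan says.** In the current protocol, the Quantitative bullet for the pilot RCT (Data and Specimen Management, Analysis) states: "Outcomes will be compared a) within individuals (baseline vs. postpartum) and b) between groups (retention, behavioral measures and clinical outcomes". It plans bivariable analyses, a priori subgroups by "age, diabetes type, medication use/changes, and gestational age at entry", and regression to assess the "relationship of SweetMama use to retention and other behavioral outcomes after controlling for potential confounders, such as length of exposure". Tests are two-sided at 0.05.

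The design section (Feasibility testing: Pilot RCT, patient component) describes randomization "with a target sample of 40 (randomized 1:3, stratified by DM type". DES-SF and PAM are collected from all women at baseline, delivery and postpartum. For A1c it says "Glycemic control will be assessed as hemoglobin A1c (final and difference from enrollment to delivery". A1c comes from serial chart values (Appendix A), and the study collects no specimens of its own.

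On exposure, the mixed-methods bullet refers to "quantity of episodes of active use, a measure of intervention exposure". The design section says "Women who are randomized to usual care will receive no orientation to or enrollment in SweetMama". Study Timelines gives all pilot women a participation span of 20 to 44 weeks, depending on gestational age at entry.

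**The concern.** The randomization is stratified by DM type, and baseline DES-SF and PAM are in hand for every woman. Yet no section names the stratum or the outcome's own baseline as an adjustment term. DM type enters the analysis only as a subgroup factor. A1c is outside the scope of the regression sentence, so its arm comparison rests on the unadjusted final value and the raw change.

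The regression that is planned leaves three things open:

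- Its regressor is use of SweetMama, which is not clearly the randomized arm.
- Its one example covariate, length of exposure, is undefined. If it means app use, it is a consequence of assignment, and adjusting for it removes part of the effect being estimated.
- Its covariate list is open-ended, so the choice can be made after the data are seen.

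In addition, the within-individual comparison does not say whether it is run by arm or pooled. What is at stake is the precision and interpretability of secondary arm differences that will be read when the full trial is designed.

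**Working it through.** **Inputs from the documents.** The target is 40 at 1:3, so 10 usual care and 30 SweetMama. The retention target is "Feasibility targets for study retention will be set at 80% retention in the study protocol", so 0.80 × 40 = 32, or 8 and 24. Two-sided 0.05.

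**Assumptions.** The documents give no SD, effect size, baseline-outcome correlation r or DM-type split. The sample size has no power basis, so there is no planned figure to reproduce. Results are in outcome SDs for r = 0.3 / 0.5 / 0.7. DM type is taken as 50:50 within each arm, with no effect of its own unless stated.

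**Standard errors at 30 vs 10**

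- Unadjusted final value: sqrt(1/30 + 1/10) = 0.365.
- Raw change: 0.365 × sqrt(2(1 − r)) = 0.432 / 0.365 / 0.283.
- Adjusted for baseline and DM type: 0.365 × sqrt((1 − r²) × 36/35) = 0.353 / 0.321 / 0.264, and 0.370 at r=0. The factor 36/35 is the price of chance baseline imbalance between arms.

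**Mean 95% CI half-widths, 20,000 simulated trials**

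| Analysis | r=0.3 | r=0.5 | r=0.7 |
|---|---|---|---|
| 30 vs 10, unadjusted | 0.734 | 0.734 | 0.734 |
| 30 vs 10, raw change | 0.870 | 0.734 | 0.569 |
| 30 vs 10, adjusted | 0.711 | 0.645 | 0.533 |
| 24 vs 8, unadjusted | 0.827 | 0.827 | 0.827 |
| 24 vs 8, adjusted | 0.805 | 0.732 | 0.602 |
| 30 vs 10, adjusted, 20% of baselines missing at random: complete case | 0.816 | 0.742 | 0.610 |
| same, pooled-mean imputation of baseline | 0.719 | 0.668 | 0.582 |
| same, missing-baseline indicator | 0.729 | 0.676 | 0.586 |

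At r=0 and 30 vs 10, adjustment moves the half-width from 0.735 to 0.746.

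**Equivalent extra patients**

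- Against unadjusted: 1/((1 − r²) × 36/35) − 1 = 6.8% / 29.6% / 90.6%.
- Against raw change: 2(1 − r)/((1 − r²) × 36/35) − 1 = 49.6% / 29.6% / 14.4%.

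**Break-even against unadjusted.** With DM type balanced across arms, r = sqrt(1 − 35/36) = 0.167. If DM type is treated as a covariate that may be imbalanced, the factor is 37/35 and, with the wider t quantile, break-even is about 0.24 (0.27 at 24 vs 8). The cost at r=0 is then 0.02 to 0.03 SD. Stratified randomization should keep the trial nearer the balanced case.

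**If DM type does predict the outcome.** Suppose the strata differ by 1 SD (assumed) and r=0.5. The unadjusted half-width is 0.829 with type I error about 2.6%. Adjusted for baseline and DM type, it is 0.648 with type I error about 5%.

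**Length of exposure.** Read as app use, it is zero in usual care by design. Read as time on study, uniform over 20 to 44 weeks in both arms, the variance inflation factor for arm is 1.01, so it costs almost no precision.

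**The case against.** The strongest reply is that nothing turns on this. The sample size text says the study does not test hypotheses and the pilot was not sized for clinical outcomes. DES-SF, PAM and A1c are secondary, and the numeric targets are 80% retention and 80% active use. Moving a half-width from 0.73 to 0.71 or 0.65 SD changes no stated decision. That stands, and it limits the point to a suggestion.

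The plan also goes part of the way. The open covariate list permits baseline adjustment of DES-SF and PAM, and the A1c change already uses baseline. This is true, but permitted is not specified. Raw change is also less precise than adjustment at all three assumed correlations, although the margin narrows as r rises.

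The size is wholly assumed, from 7% to 91% more patients, and is negative below break-even. This stands. Both the gain and the cost must be read as ranges.

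For A1c the gain is not assured, because enrollment values come from the chart. With 20% missing, complete-case adjustment gives up the gain at r=0.3 and 0.5. That can be handled by keeping those women in the model. A missing final A1c is a separate problem that baseline adjustment does not solve.

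Finally, the mixed-methods bullet does not define the regression's exposure covariate, so the harm from adjusting for app use holds only under one reading. The same sentence covers retention, so the ambiguity reaches the retention regression too, though not the 80% retention target itself.

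**Conclusion.** The point holds as a low-severity improvement. No section names the outcome's baseline or DM type as an adjustment term, and A1c has no adjusted model at all. At the target of 30 vs 10, adjustment narrows the mean 95% CI from ±0.73 SD to between ±0.71 and ±0.53 SD for r from 0.3 to 0.7. The gain would be larger if DM type itself predicts the outcome. Below a break-even r of about 0.17 to 0.24 there is a loss of at most 0.01 to 0.03 SD.

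These figures rest on assumed correlations and an assumed even DM-type split. The trial stays imprecise for these outcomes either way, and the primary feasibility and satisfaction outcomes are not affected. Confidence is medium, because r is not in the documents.

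**What to change.** In the Quantitative bullet for the pilot RCT:

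1. Estimate the arm difference in DES-SF and PAM (delivery and postpartum, each separately) and in A1c (delivery) by a linear model on randomized arm, the outcome's baseline value and DM type, with a 95% CI. For A1c, make this the main estimate in place of the raw-difference comparison.
2. Keep women without an enrollment A1c by pooled-mean imputation of the baseline or a missing-baseline indicator.
3. State that the arm contrast is by randomized assignment and is not adjusted for app use. If length of exposure is meant as time available on study, use gestational age at entry, which is known at randomization and is already a planned subgroup factor.
4. Present within-individual changes by arm, and do not read them as evidence of benefit from the app.

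The cost is analysis wording only, with no new data, visits or patients. The statistical price is two covariates, worth about 0.01 SD of half-width (up to 0.03 SD if DM type is imbalanced) when baseline does not predict the outcome.
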